EVO by DEI using CYA demonstrated higher hemostasis and lower bleeding rates compared to band ligation or sclerotherapy. Nevertheless, CYA treatment is known to be associated with significant adverse events like para-variceal injection, hemorrhage from post injection ulcer, needle sticking in the varix, intra-peritoneal injection leading to peritonitis and adherence of the glue to the endoscope, fever, embolization into the renal vein, IVC, pulmonary or systemic vessels. (**Belletrutti et al., 2008**).

Pulmonary embolism due to CYA therapy is a serious complication and sometimes fatal. Pulmonary embolism appears to be more common in patients receiving a higher volume of cyanoacrylate during the injection procedure (**Hwang et al., 2001**).

In recent years, the role of endoscopic ultrasound (EUS) has expanded rapidly into the therapeutic arena. EUS offers unique access to abdominal arterial and venous vasculature that until now has only been accessible to surgeons and/or interventional radiologists. This has had the most clinical impact on the treatment of gastroesophageal varices, where EUS may play a role both in the acute and elective management and can deliver therapy in the form of glue injection, endovascular coil placement or a combination of the two (**Hall et al., 2017**).

EUS enables an assessment using Doppler to confirm vessel obliteration after treatment. However, targeting the perforating feeder vessel rather than the varix lumen itself may theoretically minimize the amount of CYA needed to achieve obliteration of GVs and thereby reduce the risk of embolization (**Wang et al., 2016**).

Romero-Castro et al. assessed the efficacy of EUS-guided CYA injection at the entrance of the perforating veins to obtain variceal obliteration in five consecutive GV patients. They thought that EUS-guided CYA injection at the perforating veins of GV would be the optimal place to do so. This produces the maximal blood flow blockage of the inflow vein with lower amounts of CYA used and avoid either more punctures or more amounts of CYA necessary to fill the varix from the inflow to the outflow veins (**Romero-Castro et al., 2007**).

To the best of our knowledge, no studies in the literature compared standard DEI to EUS guided CYA injection into perforating veins in high risk gastric varices which represents a significant clinical challenge as it requires injection of large amount of CYA & multiple sessions which is associated with high incidence of complications.

Aim of work

The aim of present study is to compare the efficacy & safety of EUS-guided CYA injection at the entrance of the varix or the perforating veins versus DEI of CYA in treatment of high risk gastric varices.

Patients & Methods

1. Study design & Characteristics:

A single-centre, pilot randomized trial study with two arms; will be carried on patients over 1 year study period starting from June 2019 to June 2020 at the EUS Unit of the Department of Gastroenterology at Mansoura Specialized Medical Hospital, Mansoura University (Egypt).

2. Patients:

A total of 42 patients will be included, GVs will be classified according to the Sarin and Kumar classification (**Sarin and Kumar, 1989**) into GOV II or IGV I with recently bleeding GV & high-risk GV (defined by Baveno VI consensus for primary prophylaxis). After obtaining consent, eligible patients will be randomized in 2 groups using computer-generated random number sequences using excel software in concealed envelopes with block randomization design. Group I will undergo EUS-guided CYA injection at entrance of perforator veins. Group II will undergo DEI of CYA.

i. Inclusion criteria:

- Above 18 years old patients
- High risk GOV II and IGV I varices (>10 mm) on initial standard diagnostic upper endoscopy
- Recent bleeding and primary prophylaxis
- Patients who are unable or unwilling to undergo alternative therapies for GV [such as transjugular intrahepatic portosystemic shunts (TIPS) or surgery], or prior TIPS had failed.

ii. Exclusion criteria :

- Inability to give informed consent for the procedure.
- Concurrent hepatorenal syndrome and/or multiorgan failure.
- Presence of HCC &/or portal vein thrombosis.
- Previous endoscopic treatment for GVs.

- Platelet count less than 50,000/ml or International Normalized Rate (INR) >2
- Esophageal stricture
- Previous esophageal or gastric surgery.
- Pregnancy.

iii. Sample size

Sample size was calculated by PASS software for Windows (version 11.0.8).

The reported rate of obliteration of fundic varices after CA injection is high (90%) in control group (**Martínez-González et al., 2015**), and we hypothesized this rate to be 99% in EUS group.

Group sample sizes of 201 in group one (EUS group) and 201 in group two (control group) achieve 99% power to detect a difference between the group proportions of 0.1000. The proportion in group one (the treatment group) is assumed to be 0.9000 under the null hypothesis and 1.0000 under the alternative hypothesis. The proportion in group two (the control group) is 0.9000. The test statistic used is the one-sided Z test with pooled variance. The significance level of the test was targeted at 0.0100 .

According to **Connelly (2008)**, a pilot study sample should be 10% of the sample projected for the larger parent study.

For this current pilot study, it will be conducted on 10% of these admissions, so we need 21 cases for this pilot study in each arm (case and control groups).

3. Outcomes:

The primary outcome of the study will be to compare the technical success defined as complete variceal obliteration and complications rate including bleeding, pulmonary embolism (PE), ulcers, fever, paravariceal

injection & rebleeding. Secondary endpoints will be amount of cyanoacrylate used & number of sessions.

4. Methods:

Each patient will be subjected to :

- Written informed consent will be obtained from each patient, including a discussion on the procedure.
- Clinical assessment including history taking and physical examination
- Routine laboratory investigations including complete blood picture and serum creatinine.
- Liver function profile (serum bilirubin, AST, ALT , albumin and prothrombin time).
- The severity of underlying disease will be assessed by the Child–Turcotte–Pugh score (CTP) based on serum albumin, bilirubin, prothrombin time, the presence of ascites and encephalopathy.
- All procedures will be performed under deep sedation or general anesthesia in the left lateral position.
- Intravenous antibiotics will be administered to all patients prior to the endoscopic procedure to minimize the risk of secondary bacterial infection. Oral or intravenous antibiotics will be continued for at least 3 days following variceal injection.

✓ Endoscopic procedure and technique:

- Standard diagnostic upper endoscopy will be performed in order to classify the varices according to the classification of Sarin and Kumar. Only high risk GOV II and IGV I varices (>10 mm) will be included.
- EUS examination will be done in all patients with a Pentax linear Echoendoscope EG3870UTK (PENTAX medical, Tokyo, Japan) attached to a Hitachi Avius ultrasound system (Hitachi Medical Systems, Tokyo, Japan). All EUS examinations will be done by two endosonographers. The echoendoscope will be positioned in the

distal esophagus at the level of the cardia to visualize the gastric fundus and intramural varices.

- EUS will be used to display the vascular anatomy, in particular the feeding vein. GVs will be classified endosonographically according to Boustière et al which considered size of GVs and gastric wall abnormalities (**Boustière et al., 1993**):

1: Size of GVs:

- Grade 0 (none)
- Grade 1 (small or non-confluent varices < 5 mm)
- Grade 2 (large or confluent varices \geq 5 mm)

2: Abnormalities of gastric wall:

1. Grade 0 (none)
2. Grade 1 (thickening and brilliance of the third hyperechogenic layer with or without fine internal anechogenic structures).
3. Grade 2 (visible vessels in the third layer which deform the entire wall, with penetrating varices).

- EUS-guided injection of CYA will be done at entrance of of the varix or the perforator veins when identifiable using a mixture (1:1) of 2-octyl-cyanoacrylate & lipidol using 19G EUS-FNA needle in Group I, or DEI of CYA in Group II.

✓ Follow-up after endoscopy:

After the procedure, patients will be observed for 2 hours in the recovery room before being discharged. Endoscopic examination and Doppler EUS will be repeated in all patients at 3, and 6 months post-procedure (or sooner with recurrent bleeding) to confirm eradication. Hemostasis, early post treatment bleeding and late post treatment bleeding will be recorded according to Baveno VI consensus.

GVs will be considered obliterated by direct endoscopy when not visible and/or hardened to catheter palpation. Obliteration by Doppler EUS will be considered by visualization of clot and absence of Doppler

flow within the gastric wall. Repeat injection will be performed in the absence of obliteration. Direct endoscopic and Doppler EUS examinations will be repeated again at 3, and 6 months after each injection.

[figure not shown]
Ethical considerations:

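### The platelet limit in the exclusion criteria is written per ml; taken literally this equals 50 per microlitre, and that limb would exclude no one

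*Protocol*

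**What the plan says.** In the Protocol, section 2 (Patients), part ii (Exclusion criteria), one bullet sets two laboratory limits joined by an or: "Platelet count less than 50,000/ml or International Normalized Rate (INR) >2". They are the only numerical blood-test limits in the exclusion list.

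The platelet limit appears nowhere else. The only other reference to blood counts is in section 4 (Methods), which lists "Routine laboratory investigations including complete blood picture and serum creatinine" and gives neither a platelet value nor a reporting unit. So no other part of the protocol corrects or overrides the per-ml unit.

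**The concern.** The stated number and the stated unit do not work together as an exclusion. Per ml, the limit is 1,000 times lower than the same number per microlitre, and on any ordinary range of platelet counts no candidate would fall below it.

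An exclusion criterion should be applicable, and open to audit, as written. Here a reader who follows the text exactly finds every platelet count acceptable. A reader who takes the number in some other unit excludes patients whom the text does not exclude. The rule also has a safety purpose: it governs entry to a trial of variceal injection in which bleeding and rebleeding are part of the primary outcome (section 3, Outcomes).

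**Working it through.** **Inputs**

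- Platelet limit: 50,000 per ml (Protocol, Exclusion criteria).
- Second limb of the same bullet: "International Normalized Rate (INR) >2", joined by or (same place).
- Candidates' platelet counts: not given in the documents. Assumed to lie between 5,000 and 500,000 per microlitre, a deliberately wide range.

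The protocol states the limit without any derivation, so there is no calculation of its own to reproduce. The check is a conversion of units.

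**Step 1: convert the limit**

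- Per microlitre: 50,000 per ml ÷ 1,000 microlitres per ml = 50 per microlitre.
- Per litre: 50,000 per ml × 1,000 ml per litre = 50,000,000 per litre = 0.05 x 10^9 per litre.

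**Step 2: compare with the assumed range**

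| Assumed count per microlitre | Same count per ml | Ratio to 50,000 per ml |
|---|---|---|
| 5,000 | 5,000,000 | 100 |
| 500,000 | 500,000,000 | 10,000 |

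Every count in the range is at least 100 times the written limit, so the platelet limb excludes 0% of candidates within it. For the limb to exclude anyone, a count would have to be below 50 per microlitre, which is one hundredth of the bottom of the assumed range.

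**Step 3: the other limb**

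INR has no volume unit and is not affected. Because the limbs are joined by or, a patient with INR above 2 is still excluded whatever the platelet limb does.

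**Step 4: does it reach the sample size?**

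The protocol states that "Group sample sizes of 201 in group one (EUS group) and 201 in group two (control group) achieve 99% power", and adds "The significance level of the test was targeted at 0.0100". With proportions 1.00 and 0.90, their mean 0.95, a one-sided Z test with pooled variance and z = 2.326 for both alpha 0.01 and power 0.99:

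n = [2.326 × √(2 × 0.95 × 0.05) + 2.326 × √(1.00 × 0 + 0.90 × 0.10)]² ÷ 0.10²

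= [2.326 × (0.3082 + 0.3000)]² ÷ 0.01 ≈ 2.00 ÷ 0.01 ≈ 200.2, rounded up to 201 per arm.

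The stated 201 is reproduced without any platelet input. The unit therefore has no bearing on sample size, alpha or power.

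**The case against.** The strongest reply is that this is a slip that misleads nobody. By the argument above the literal limit can exclude no one, so it is not a rule that staff would screen by. They would apply the number in the unit their laboratory reports. The trial runs in one unit at one centre with 42 patients, so differences between sites do not arise. The criterion also acts before randomisation and on both arms alike, so misapplying it would not by itself bias the comparison. Most of this stands, and it is why the practical effect is probably small. It does not make the text right: the criterion works only if the reader discards the stated unit and supplies another. An eligibility threshold belongs in the protocol and is not a detail to be left to an analysis plan.

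A second reply is that a micro sign may have been misread when the text was taken from PDF. This cannot be ruled out from the text. The line is complete and shows no sign of garbling, but the micro sign occurs nowhere else, so there is nothing to compare it with. A look at the source page settles it.

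Three stronger readings may tempt a reader, and the documents support none of them.

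- That the whole criterion excludes nobody. The INR limb still excludes patients.
- That 0% is a figure from the protocol. It rests on the assumed range of counts, although it would hold for any range whose lowest count is at least 50 per microlitre.
- That screening was inconsistent, or that patients were wrongly randomised. With 21 patients per arm, each is 1/21 = 4.8% of an arm, so a disputed case would show, but nothing in the protocol indicates that any dispute arose or is likely.

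**Conclusion.** The point holds for the platelet limb only. As written the limit is 50 per microlitre (0.05 x 10^9 per litre), a factor of 1,000 below the same number per microlitre. On the assumption that candidates' counts lie between about 5,000 and 500,000 per microlitre, this limb excludes no one. The conclusion also assumes that the source page does say per ml.

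It is most likely a slip in the unit. The effect on the trial is small if screening already uses the laboratory's usual unit, and the design calculations are untouched. It still merits correction, because a stated exclusion with a safety purpose does not work when followed exactly.

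**What to change.** First check the source page of the protocol to confirm that it says per ml. If it does, the investigator should confirm the intended platelet threshold. Number and unit should then be restated together in the unit the laboratory reports, and the same expression used on the screening form. Which value is intended is for the investigator to say; none is proposed here.

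The cost is a one-word correction to the protocol. If screening already uses the intended unit, practice does not change. Nothing in the sample size or the analysis needs to be revisited.

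### The protocol hypothesizes 99% versus 90% obliteration, but its 201 per arm at 99% power, and the 21 per arm taken from it, were computed for 100% versus 90%

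*Protocol*

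**What the plan says.** All of this is in the Protocol, section 2.iii (Sample size), apart from the total enrolment.

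- **Hypothesis.** Control obliteration is put at 90%. For the new technique: "we hypothesized this rate to be 99% in EUS group".
- **Calculation.** 201 per arm are said to "achieve 99% power to detect a difference between the group proportions of 0.1000". The EUS proportion "is assumed to be 0.9000 under the null hypothesis and 1.0000 under the alternative hypothesis", and the control proportion is 0.9000.
- **Test.** "The test statistic used is the one-sided Z test with pooled variance", at a significance level of 0.0100.
- **Pilot size.** The protocol cites a rule that "a pilot study sample should be 10% of the sample projected for the larger parent study". It says of the present study that "it will be conducted on 10% of these admissions", "so we need 21 cases for this pilot study in each arm".
- **Enrolment.** Section 2 (Patients) fixes the total: "A total of 42 patients will be included".

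**The concern.** Two consecutive paragraphs give different EUS rates, 99% and 100%. Rounding does not explain this. The calculation is printed to four decimals, so 99% would appear as 0.9900, and the printed difference of 0.1000 independently confirms 1.0000. No other part of the protocol reconciles the two.

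One percentage point matters here because the rates are near the ceiling. At exactly 100% the EUS arm contributes no variance under the alternative. At 99% it does, and the difference to be detected is also smaller.

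This is the protocol's only sample-size justification. The 99% power, the parent size of 201 per arm and the pilot's 21 per arm all belong to a larger effect than the one hypothesized. A later full trial that reused 201 would carry the mismatch forward.

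**Working it through.** **Inputs (all from section 2.iii).** Control rate p2 = 0.90. EUS rate p1 = 1.00 in the calculation, 0.99 in the hypothesis. One-sided alpha 0.01, so z_a = 2.3263. Power 99%, so z_b = 2.3263. Equal arms, pooled-variance Z test. The pilot is 10% of the parent size.

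**Formulas.** With d = p1 − p2 and p̄ = (p1 + p2)/2:

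- A = √(2p̄(1 − p̄)) and B = √(p1(1 − p1) + p2(1 − p2))
- n per arm = ((z_a·A + z_b·B)/d)²
- power at n = Φ((d√n − z_a·A)/B)

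**Step 1: the protocol's own figure (1.00 vs 0.90).** p̄ = 0.95, A = 0.3082, B = 0.3000, d = 0.10.

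- n = ((0.7170 + 0.6979)/0.10)² = 200.20, rounded up to **201**
- Power at 201 = Φ((1.4177 − 0.7170)/0.3000) = Φ(2.336) = **99.0%**

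Both published figures reproduce, so 100% is the rate that was entered.

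**Step 2: the stated hypothesis (0.99 vs 0.90), other inputs unchanged.** p̄ = 0.945, A = 0.3224, B = 0.3161, d = 0.09.

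- n = ((0.7500 + 0.7353)/0.09)² = 272.37, rounded up to **273** (273/201 = 1.36, or 36% more)
- Power at 201 = Φ((1.2760 − 0.7500)/0.3161) = Φ(1.664) = **95.2%**
- Check: power is 98.99% at 272 and 99.01% at 273

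**Step 3: does the shortfall depend on the approximation?** The normal approximation is rough this close to 100%. The same rejection rule was therefore evaluated by summing the binomial probabilities of every outcome that rejects.

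- 0.99 vs 0.90, 201 per arm: **98.2%** power (actual one-sided size at 0.90 vs 0.90 is 0.0101)
- 0.99 vs 0.90: 98.98% at 221 and 99.01% at 222, so **222** per arm for 99% power

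The shortfall is smaller but remains. The 222 is not on the same footing as the protocol's 201: by exact enumeration, 1.00 vs 0.90 would need only 127 per arm. The like-for-like pairs are 201 with 273 (normal approximation) and 127 with 222 (exact).

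**Step 4: the pilot.** The protocol takes 10% of 201 = 20.1 and rounds up to 21.

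| Basis | Parent n per arm | 21 as a share | 10% rule, rounded up | Total |
|---|---|---|---|---|
| 1.00 vs 0.90, as calculated | 201 | 10.4% | 21 | 42 |
| 0.99 vs 0.90, normal approximation | 273 | 7.7% | 28 | 56 |
| 0.99 vs 0.90, exact | 222 | 9.5% | 23 | 46 |

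**The case against.** The strongest reply is that this changes little in the trial that will be run. It is a pilot, no power is claimed for 42 patients, and 21 per arm comes from a rule of thumb. Even the projected parent trial would keep about 95% power (98% exact) at 201 per arm under the stated hypothesis. That stands, and it is why the point is minor.

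Second, the calculation is coherent in itself, and the odd item may simply be the 99% in the prose. If so, one number is wrong and the rest holds. That is possible, but the document does not show which rate was meant. The 28 or 23 per arm in the table are therefore conditional on keeping 99% and do not show a shortfall in recruitment.

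Third, setting an exact parent size of 222 beside the protocol's 201 mixes two methods and makes the gap look like about 10%. This is fair. The like-for-like comparison is 201 with 273. The exact figures are given because they show that the 99% claim also fails without the approximation.

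None of this removes the contradiction between the two paragraphs.

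**Conclusion.** The concern holds and is minor. The stated 99% power and 201 per arm belong to 100% versus 90%, not to the hypothesized 99% versus 90%. Under the stated hypothesis 201 per arm gives 95.2% power (98.2% exact). The 21 per arm is then not 10% of the size needed for 99% power.

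This rests on the protocol's own settings: one-sided alpha 0.01, pooled Z test, equal arms and a 90% control rate. It assumes nothing about which EUS rate was intended, only that the same rate should appear in the hypothesis and in the calculation.

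**What to change.** Use one EUS rate throughout section 2.iii. Either option will do.

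1. **If 100% was meant:** change the hypothesis sentence from 99% to 100%. The 201 per arm, the 99% power, the 10% rule and 21 per arm then all stand. Cost: one number in one sentence.
2. **If 99% was meant:** replace 1.0000 with 0.9900 and 0.1000 with 0.0900. Restate the power of 201 per arm as about 95% (about 98% exact), and give 273 per arm (222 exact) as the size for 99% power. Naming one method and using its figures throughout is enough. Keep 42 patients and say openly that 21 per arm is 7.7% (9.5% exact) of that size, whereas the cited rule would give 28 (23 exact). Cost: the figures in one paragraph, one added sentence and a less favourable stated power.

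More patients would be needed only if the sponsor keeps 99% and also applies the 10% rule literally: 56 − 42 = 14 more, or 46 − 42 = 4 more by exact enumeration. No endpoint or procedure changes under either option.

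### The primary complications rate counts undefined bleeding and rebleeding together with injection harms, so a difference in variceal rebleeding can show up as a difference in safety

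*Protocol*

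**What the plan says.** Protocol, section 3 (Outcomes), has a two-part primary outcome. It opens: "The primary outcome of the study will be to compare the technical success defined as complete variceal obliteration and complications rate including bleeding". The safety half is a "complications rate including bleeding, pulmonary embolism (PE), ulcers, fever, paravariceal"; the list then runs over a page break, and its last items are "injection & rebleeding". The complications rate therefore holds bleeding, pulmonary embolism (PE), ulcers, fever, paravariceal injection and rebleeding. Bleeding and rebleeding are separate items, and neither is defined.

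Four other places bear on this:

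- The Aim of work sets efficacy and safety as two things to compare.
- The background cites bleeding as a measure of benefit: "EVO by DEI using CYA demonstrated higher hemostasis and lower bleeding rates compared to band ligation or sclerotherapy". Its list of adverse events of the glue has one bleeding item, haemorrhage from an ulcer after injection. Variceal rebleeding is not on that list.
- Section 4 (Methods), follow-up after endoscopy, schedules examinations at 3 and 6 months, "or sooner with recurrent bleeding) to confirm eradication". It adds: "Hemostasis, early post treatment bleeding and late post treatment bleeding will be recorded according to Baveno VI consensus". This classifies bleeding by time, not by source.
- Section 2.i admits both kinds of patient: "Recent bleeding and primary prophylaxis".

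**The concern.** Variceal rebleeding is largely what obliteration is meant to prevent, while PE, ulcers, fever and paravariceal injection are harms of delivering the glue. If they share one rate, that rate responds to both. The sponsor expects better obliteration with EUS. If that brings fewer variceal rebleeds, the EUS complications rate falls for an efficacy reason and can be reported as better safety. The opposite error is also possible: fewer rebleeds can offset a real excess of injection harm in the same arm.

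The undefined labels add to this. In a patient enrolled with recent bleeding, one haemorrhage after treatment fits both bleeding and rebleeding. In a primary-prophylaxis patient, a first haemorrhage after treatment is not a rebleed in the ordinary sense, though a second could be. The early and late categories in the follow-up section are not tied to either label.

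**Working it through.** **The plan's own figure.** The only calculation (section 2.iii) concerns obliteration: 90% versus 100%, one-sided Z test with pooled variance, alpha 0.01, power 99%. With a mean proportion of 0.95 and z = 2.326 for both alpha and power:

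n = [2.326 × √(2 × 0.95 × 0.05) + 2.326 × √(0.90 × 0.10 + 0)]² / 0.10² = [2.326 × (0.308 + 0.300)]² / 0.01 ≈ 200.2

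This rounds up to the stated 201 per arm. Ten per cent is 20.1, hence 21 per arm. No complication or rebleeding rate enters the calculation, so the point below does not depend on it.

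**Inputs for the check.** From the document: hypothesised obliteration of 99% (EUS) and 90% (direct endoscopic injection, DEI), and 21 patients per arm. Assumed, because the document gives no figure: injection harm h of 10%, 20% or 30%, equal in both arms; harm and rebleeding independent; the complications rate read as the share of patients with any listed event.

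**Upper bound through obliteration alone.** Rebleeding differs most if every non-obliterated patient rebleeds and no obliterated patient does: r = 1% (EUS) versus 10% (DEI), a 9-point difference.

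Pooled rate = 1 − (1 − h)(1 − r); gap = (1 − h) × (0.10 − 0.01)

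| h, both arms | EUS | DEI | Gap |
|---|---|---|---|
| 10% | 1 − 0.90 × 0.99 = 10.9% | 1 − 0.90 × 0.90 = 19.0% | 8.1 points |
| 20% | 1 − 0.80 × 0.99 = 20.8% | 1 − 0.80 × 0.90 = 28.0% | 7.2 points |
| 30% | 1 − 0.70 × 0.99 = 30.7% | 1 − 0.70 × 0.90 = 37.0% | 6.3 points |

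The true difference in injection harm is zero in every row. If only half of the non-obliterated patients rebleed, the gaps halve to about 4.1, 3.6 and 3.2 points. With the 100% that the sample-size calculation uses for EUS, the bound is 10 × (1 − h), or 7 to 9 points.

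**Offset.** With the same rebleeding risks, the pooled rates are equal when (1 − h_EUS) × 0.99 = (1 − h_DEI) × 0.90. For h_DEI = 20%, h_EUS = 1 − 0.72/0.99 = 27.3%. An excess of 7.3 points in injection harm would leave no trace in the pooled rate.

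**At 21 per arm.** A gap of 7.2 points is 0.072 × 21 ≈ 1.5 patients. By exact binomial enumeration, EUS shows the numerically lower pooled rate with probability 70%, 64% and 61% for h = 10%, 20% and 30%, against 40%, 42% and 43% when only injection harms are counted (the rest is ties or DEI lower). A Fisher exact test at two-sided 0.05 favours EUS with probability 5.6%, 4.1% and 3.1%, against about 1% for injection harms alone.

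**The case against.** The best defence has four parts.

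- *The text does not fix a pooled any-event rate.* This stands. The list could be tabulated item by item, and a statistical analysis plan not shown here may say so. Item-by-item reporting would lessen the problem. It would not settle what bleeding and rebleeding mean, or move rebleeding out of the primary complications.
- *Some bleeding after injection is a harm.* This stands. A reader might infer that every rebleed is treatment failure. The background contradicts that, since it lists ulcer haemorrhage as an adverse event. The follow-up section does not say it either: confirming eradication is the purpose of the scheduled examinations, and recurrent bleeding only changes their timing. Simply deleting rebleeding would therefore be wrong; the source has to be separated.
- *Large distortions are not supported.* This stands. One can construct a 12-point gap (harm of 20% in both arms, rebleeding of 5% versus 20%, giving 24% versus 36%), but that needs a 15-point difference in rebleeding. Final obliteration of 99% versus 90% cannot supply more than 9.
- *The mapping between the bleeding schemes cannot be fully judged.* This stands in part, because the follow-up section defers to consensus definitions that are not reproduced. But section 3 does not refer to that scheme.

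**Conclusion.** The concern holds as a defect in how the primary outcome is composed. Efficacy-type and harm-type bleeding share one complications rate under two undefined labels, although the protocol asks about efficacy and safety separately. If the rate is used as one figure, a difference in variceal rebleeding becomes a difference in apparent safety or offsets a real one.

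Through obliteration alone the spurious gap is at most about 6 to 8 points, under the assumed harms of 30% to 10%, independence and the extreme rebleeding pattern above. Larger gaps need a further assumed route, such as bleeding before obliteration is reached, for which the protocol gives no rate. The distortion requires rebleeding to differ between arms.

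Three stronger conclusions might be inferred and are not supported. A false significant safety result is not the main risk: within the bound it occurs about 3% to 6% of the time, so the likelier damage is a misleading estimate. PE is a named item, so the embolism question is not left unanswered, only at risk of being obscured in a pooled figure. And primary-prophylaxis patients can rebleed once they have had a first haemorrhage; the difficulty is that the label means different things in the two groups enrolled.

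**What to change.** In section 3 (Outcomes):

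1. Take recurrent variceal bleeding out of the complications rate and report it as an efficacy outcome, using the early and late post-treatment bleeding that the follow-up section already records.
2. Keep bleeding from an injection ulcer in the complications rate, with PE, ulcers, fever and paravariceal injection.
3. Assign each haemorrhage to one category only, by the source seen at the endoscopy that the follow-up section brings forward for recurrent bleeding. Show haemorrhages of unclear source separately.
4. Report post-treatment bleeding separately for patients enrolled with recent bleeding and for primary prophylaxis.
5. Show PE on its own line, so that commoner items such as fever cannot obscure it.

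The cost is protocol wording, a few table rows and one added data item, the bleeding source. No visit or procedure is added. The complications rate will contain fewer events and be slightly less precise, and some haemorrhages may stay unclassified.

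### The EUS size scale has its top grade at 5 mm and above, but entry requires more than 10 mm, so it carries almost no information on varix size

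*Protocol*

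**What the plan says.** The size threshold for entry appears twice in the Protocol. Section 2.i (Inclusion criteria) asks for "High risk GOV II and IGV I varices (>10 mm) on initial standard diagnostic upper endoscopy". Section 4 (Methods, Endoscopic procedure and technique) repeats it: "Only high risk GOV II and IGV I varices (>10 mm) will be included".

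The same part of section 4 provides for EUS in both arms ("EUS examination will be done in all patients with a Pentax linear Echoendoscope EG3870UTK") and classifies the varices by a published scheme "which considered size of GVs and gastric wall abnormalities". Its size part has three levels: Grade 0 for none, then "Grade 1 (small or non-confluent varices < 5 mm", then "Grade 2 (large or confluent varices \geq 5 mm". The gastric-wall part is a separate grade and does not measure diameter. The Sarin and Kumar classification is used to sort varices into GOV II or IGV I, and the Protocol gives no size levels for it. No baseline diameter in mm is requested, either of the varix or of the feeding vein that EUS is meant to display.

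Section 2 describes allocation by "computer-generated random number sequences using excel software in concealed envelopes with block randomization design" and names no stratification factor. Section 3 (Outcomes) states: "Secondary endpoints will be amount of cyanoacrylate used & number of sessions". Section 2.iii (Sample size) sets 21 patients per arm.

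**The concern.** The entry threshold is twice the lower limit of the top size grade. A 12 mm varix and a 35 mm varix both meet the entry criterion and receive the same grade. The scale was built to separate small varices from large ones, and the trial has already excluded the small ones.

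This matters because of the two secondary endpoints. The introduction argues for injection at the perforating vein on the ground that it takes less cyanoacrylate than filling the whole varix. That ties the glue needed for direct injection to how much varix there is to fill. Size is thus a natural prognostic variable for glue amount, and plausibly for number of sessions. In a trial of 42 patients, readers will want to know whether the arms were alike in size. A baseline table showing nearly everyone at Grade 2 in both arms would look like balance, when it says only that both arms met the entry criterion.

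**Working it through.** **Inputs.** From the Protocol: entry above 10 mm (sections 2.i and 4); Grade 1 below 5 mm and Grade 2 from 5 mm upwards (section 4); 21 per arm (section 2.iii). Assumed, because the documents give no figure: the measurement error between endoscopy and EUS, and the correlation r between varix size and glue amount.

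**The plan's own sample size.** For proportions 0.90 and 1.00, one-sided alpha 0.01, 99% power and a pooled Z test:

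n = [2.326 × √(2 × 0.95 × 0.05) + 2.326 × √(0.90 × 0.10 + 1.00 × 0)]² / 0.10² = (0.717 + 0.698)² / 0.01 ≈ 200.2, so 201 per arm.

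This agrees with the Protocol. Ten per cent is 20.1, rounded up to 21 per arm. The point here uses only the 21.

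**Step 1: eligible sizes mapped onto the grade.** Diameters of 10.1, 12, 15, 20, 30 and 40 mm all give Grade 2.

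**Step 2: how an enrolled patient could be Grade 1.** Entry is read on endoscopy and the grade on EUS, so the two could disagree. The under-reading needed to fall below 5 mm is 1 − 5/d:

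- d = 10.1 mm: more than 50%
- d = 12 mm: more than 58%
- d = 15 mm: more than 67%
- d = 20 mm: more than 75%

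With a normal between-method error of assumed SD 1, 2 or 3 mm, the probability of a reading below 5 mm is Φ((5 − d)/SD). At d = 10.1 mm this is about 0%, 0.5% and 4.5%. At 15 mm it is below 0.1% throughout. A Grade 1 would mostly reflect disagreement between methods.

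**Step 3: chance imbalance in diameter.** In units of the between-patient SD, the standard error of the difference in mean size between arms is √(1/21 + 1/21) = √(2/21) = 0.309. Then:

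- 95% range: ± 1.96 × 0.309 = ± 0.60 SD
- P(difference above 0.25 SD, either direction) = 2 × [1 − Φ(0.25/0.309)] = 0.418
- P(difference above 0.5 SD, either direction) = 2 × [1 − Φ(0.5/0.309)] = 0.105

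**Step 4: what such an imbalance does to glue amount.** If r is 0.5 to 0.7 (assumption), a 0.5 SD imbalance in size moves the observed difference in glue amount by 0.5 × r = 0.25 to 0.35 SD. The standard error of that comparison is also 0.309 SD, so the shift is about 0.8 to 1.1 standard errors.

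**Step 5: what adjustment could gain.** Adjusting for diameter removes r² of the residual variance: 0.5² = 25% to 0.7² = 49%. The standard error is multiplied by √(1 − r²), that is 0.87 to 0.71. If size had no relation to glue amount in the EUS arm and r = 0.5 to 0.7 only under direct injection, a common slope would be r/2 (equal SDs in the arms) and would remove (r/2)² = 6% to 12%. Adjusting for a grade that is the same for everyone removes nothing.

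**The case against.** The strongest reply is that the Protocol gives the grade no role in the analysis. It is a descriptive classification, not a stratification factor, balance check or covariate. A scale that hardly varies in a selected population is uninformative, but it does not contradict the entry criterion. That stands: the two sections are compatible, and the weakness lies in the choice of measure.

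A reader might go further and infer that a difference in glue amount could not be told apart from a difference in varix size, so that the comparison is confounded. The documents do not support this. Allocation is randomised with concealed envelopes, and the unadjusted test and its confidence interval already allow for chance imbalance in size, measured or not. What is lost is precision and a descriptive check.

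A reader might also infer that the grade cannot vary at all, or that diameter will certainly go unrecorded. Neither follows. The first assumes that endoscopy and EUS agree within about a factor of two. As to the second, applying the 10 mm limit requires some judgement of size in mm, and the documents at hand include no case report form. Still, the Protocol uses that limit only as a yes/no threshold and nowhere says that the value is kept.

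Finally, the choice of covariates may be left to an analysis plan. That is fair, but an analysis plan cannot recover diameter from a grade that is nearly constant. What is measured at baseline has to be settled in the protocol.

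**Conclusion.** The point holds as a weakness in baseline measurement. On the Protocol's own limits, the stated size classification will be Grade 2 for nearly every enrolled patient, provided that endoscopy and EUS agree within a factor of two. With 21 per arm, a chance size imbalance above 0.5 SD has a probability of about 10%, and the grade would not show it. The possible gain in precision for glue amount is illustrative: 25% to 49% of residual variance if r is 0.5 to 0.7 in both arms, and less if the link is weaker under EUS-guided injection. No source for r is given in the documents.

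The reach is limited to interpretation of the two secondary endpoints of a pilot trial. Nothing here shows an effect on the primary outcome or a bias in any comparison. Minor priority.

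**What to change.** In section 4, add that at the baseline EUS, before injection, the largest varix diameter is recorded in mm in both arms, with the feeding-vein diameter when that vein is seen. Keep the 0/1/2 size grade beside it if the published scheme is wanted for description. Keep the gastric-wall grade, which can still vary.

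Report the diameter by arm in the baseline table. Prespecify varix diameter as a covariate in a supportive analysis of glue amount and number of sessions, with the unadjusted comparison beside it. Feeding-vein diameter is better left as description, since it will be missing where the vein is not seen.

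The cost is one or two fields on the form. No procedure is added and treatment is unchanged. The covariate uses one degree of freedom, leaving 39 instead of 40 residual degrees of freedom with 42 patients (42 − 2 = 40; 42 − 3 = 39).
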